7.2.2.2 Secondary Outcomes

7.2.2.2.1 11-point numeric rating scale (NRS-11)

Time Frame: Change from Baseline at 1 day, 3 days, 1 week, 2 weeks, 3 weeks and 4 weeks, one-month follow-up after treatment

7.2.2.2.2 Visual analogue scale (VAS)^{8,9}

A horizontal line 10cm long (or 100mm), one end of the horizontal line indicates no pain (0); the other end indicates the most severe pain imaginable (10); the middle part indicates different degrees of pain. Ask the subjects to draw a vertical line mark at the place closest to their pain level to quantify the intensity of their pain.

no pain worst imaginable pain

Time Frame: Change from Baseline at 1 day, 3 days, 1 week, 2 weeks, 3 weeks and 4 weeks, one-month follow-up after treatment

7.2.2.3 Verbal rating scale (VRS)⁷

According to the grading method used to assess the degree of pain in the subject, the evaluator divided the degree of pain in the subject from no pain to severe pain, which is relatively simple and has a good correlation with NRS. VRS was scored with "no pain" = 0, "mild pain" = 1, "moderate pain" = 2, and "severe pain" = 3.

- Level 0: No pain.
- Level I (mild): Pain, but tolerable, can live a normal life, sleep is not disturbed.
- Level II (moderate): Pain is obvious, intolerable, painkillers are required, and sleep is disturbed.
- Level III (severe): The pain is severe and unbearable, analgesics must be used, sleep is severely disturbed, and it may be accompanied by autonomic disorders or passive posture.

Time Frame: Change from Baseline at 1 day, 3 days, 1 week, 2 weeks, 3 weeks and 4 weeks, one-month follow-up after treatment

7.2.2.2.4 Mechanical pain threshold (MPT)¹⁰⁻¹³

In order for the subject to focus on the sensory test, the test should be in a quiet room. After exposing the test site (select the middle position of the PHN, try to ensure that the test position is basically unchanged at subsequent time points; avoid scars and injury sites), the researcher should ask the subject to close their eyes or look away, using 20 hand-helds The Von frey filament (starting from the 2.83 specification) is applied vertically on the skin surface until the filament is bent into a 90 degree or "C" shape and remains in place for about 1.5 s. The subject indicated whether the Von frey filament caused pain by answering "yes" or "no". If the subject answers "No", use a larger diameter filament to increase the intensity application until the subject responds. After the subject answered "yes", the descending stimulus sequence was used, and the smaller diameter filament was used to reduce the intensity of the stimulation until the subject answered "no". Alternate between ascending and descending order until 5 deflection points are recorded. The final mechanical pain threshold is the geometric mean of these 5 points.

Time Frame: Change from Baseline at 1 day, 3 days, 1 week, 2 weeks, 3 weeks and 4 weeks, one-month follow-up after treatment

7.2.2.5 Pain area of PHN (PAP)^{14,15}

Refer to the scoring method of the 45 body areas rating scale.

PHN pain area = the patient's body surface area (BSA, m^2) * "pain area code" as a percentage of body surface * "PHN area" as a percentage of pain area (assessed by the investigator)

45 Body Areas Rating Scale (BARS-45)

Body surface area (BSA) BSA (m²) = $\sqrt{\text{Ht}(\text{cm}) * \text{Wt}(\text{kg})/3600}$

Pain area code	Percentage of body surface area
25, 26, 27	0.50%
4, 5, 16	1.00%
3, 8, 9, 10, 11, 30, 31, 32, 33	1.50%
1, 2, 21, 22, 23, 24, 44, 45	1.75%
6, 7, 12, 13, 28, 29, 36, 37	2.00%
38, 39	2.50%
14, 15	3.00%
19, 20, 42, 43	3.50%
34, 35	4.00%
17, 18, 40, 41	4.75%

Time Frame: Change from Baseline at 1 day, 3 days, 1 week, 2 weeks, 3 weeks and 4 weeks, one-month follow-up after treatment

7.2.2.2.6 Average number of pain episodes (ANPE)¹⁶ (Within 24 hours)

- Painless: 0 times
- Intermittent pain: 1-50 times (optional 1-2, 3-5, 6-10, 11-50)
- Persistent pain: >50 times

Time Frame: Change from Baseline at 1 day, 3 days, 1 week, 2 weeks, 3 weeks and 4 weeks, one-month follow-up after treatment

7.2.2.7 Average duration of each pain episode (ADEPE)

Duration range: 0 minutes (no pain) -24 hours (persistent pain)

Time Frame: Change from Baseline at 1 day, 3 days, 1 week, 2 weeks, 3 weeks and 4 weeks, one-month follow-up after treatment

7.2.2.2.8 Short form of McGill pain questionnaire 2 (SF-MPQ-2)¹⁷⁻²¹

It includes four dimensions: persistent pain, paroxysmal pain, neuropathic pain, and the influence on mood, with a total of 22 items (See appendix 1).

Time Frame: Change from Baseline at 4 weeks, one-month follow-up after treatment

7.2.2.2.9 Zoster brief pain inventory (ZBPI)²² (See appendix 2)

Time Frame: Change from Baseline at 4 weeks, one-month follow-up after treatment

7.2.2.2.10 Depression, anxiety and positive outlook scale (DAPOS)²³ (See appendix
3)

A reliable and brief scale that specifically evaluates the mood of patients with pain, including depression, anxiety, and positive influence, with a total of 11 items. Each item is scored 1-5, 1 point means never happening, 5 points means always happening.

Time Frame: Change from Baseline at 4 weeks, one-month follow-up after treatment

7.2.2.2.11 Patient global impression of change (PGIC)²⁴

Clinical overall impression scale, to assess whether the patient's clinical condition has improved or declined. Score 1-5, in order of obvious improvement, slight improvement, no change, slight aggravation, and obvious aggravation.

Time Frame: Change from Baseline at 4 weeks, one-month follow-up after treatment

7.2.2.2.12 Safety of electroacupuncture (SEA)

Evaluation is performed before and after each treatment. Contents include broken needles, fainting needles, unbearable acupuncture pain (VAS \geq 8 points), local hematomas, infections and abscesses; other discomforts after acupuncture (after acupuncture with a duration of 1 hour or more after the needle stick) Pain, nausea, vomiting, palpitations, dizziness, headache, anorexia and insomnia) symptoms, average severity and average duration; and other unforeseen adverse events.

This study requires patients to report adverse reactions at any time, and doctors timely record the name, frequency and duration of adverse reactions.

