5.2 Electroacupuncture (EA) group

Points selection: ipsilateral Zhigou (SJ6), Yanglingquan (GB34), and Ashi points.Location: Refer to the National Standard of the People's Republic of China "Acupoint Name and Location" (GB/T 12346-2006) for acupoint location.

Operation method: Participants take the appropriate position on the treatment bed according to the location of PHN. After routine skin disinfection, the sterile insulating adhesive pads are placed on ipsilateral Zhigou, Yanglingquan and Ashi points. Then acupuncture needles are inserted vertically into the skin of Zhigou and Yanglingquan through the pads approximately 15 to 20 mm, and performs slight, equal manipulations of twirling and lifting to reach the sensation of deqi (known as soreness, numbness, distention, heaviness or other sensations, which is considered to indicate effective acupuncture). Besides, acupuncture needles are inserted obliquely (at an angle of 30 to 45 degrees) into the skin of Ashi points through the pads approximately 10 mm, and point the needle towards the painful area of PHN. The paired poles of electroacupuncture apparatus are connected to the needle handles at ipsilateral Zhigou and Yanglingquan, and for Ashi points, the paired poles are connected to the head and tail acupoints of the long axis of the painful area. The waveform of electroacupuncture stimulation is a continuous wave with a frequency of 2 Hz and a current intensity of 1-5 mA (causing mild tremor of the skin around the acupoints without pain), and continue the electroacupuncture treatment for 30 minutes.

Frequency and duration of treatment: All patients will receive electroacupuncture treatment once per day, 5 times a week for 4 consecutive weeks (20 treatments in total).

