8.1 Observation of adverse events

Adverse events are any unexpected symptoms, signs, or health conditions during the entire clinical study period (including washout period, observation period, routine treatment period, follow-up period, a total of 10 weeks), and may not have a causal relationship with the treatment in this study. Health conditions or diseases that existed before the start of this study can only be considered as an adverse event if they deteriorate further after starting the treatment of this study. Abnormal laboratory test values or test results can only be considered adverse events (AE) when they cause clinical symptoms or signs, are considered clinically significant or require treatment. Use non-inductive questions at each visit during the study period to discover adverse events from patients. Adverse events may also be reported by the patient during or between visits or discovered through physical examination, laboratory examination or other methods. All adverse events must be recorded on the adverse events page of the CRF, and the following information about the adverse events must be provided at the same time:

- Severity (mild, moderate, severe).
- The relationship with the research treatment (definitely related, very likely related, possibly related, definitely unrelated).
- Duration (start and end dates or whether they still exist at the time of the last inspection).
- Whether it is a serious adverse event (SAE). A serious adverse event (SAE) is defined as an adverse event leading to any of the following outcomes: 1) leading to death. 2) Fatal or life-threatening. 3) Lead to permanent or significant loss of

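### The safety outcome summarises after-needling discomforts by an average severity and duration with no stated averaging unit, which can mask a participant's worst or longest reaction; use per-participant maxima from the section 8.1 fields

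*Protocol*

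**What the plan says.** Safety is part of the study objective (protocol section 2). Treatment is given "once per day, 5 times a week for 4 consecutive weeks (20 treatments in total" (section 5.2), and the sham arm follows the same treatment settings (section 5.3).

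Section 7.2.2.2.12 lists safety among the secondary outcomes and states: "Evaluation is performed before and after each treatment". It names several discrete events first (for example fainting, haematoma, infection and unbearable needling pain). It then lists other discomforts after needling, from pain and nausea to headache and insomnia, and describes them by "symptoms, average severity and average duration; and other unforeseen adverse events". No averaging unit is given: it could be all sessions, symptomatic sessions, or the course of one episode. The section closes by requiring that "doctors timely record the name, frequency and duration of adverse reactions"; severity is not in that list.

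Section 8.1 works event by event. It says "All adverse events must be recorded on the adverse events page of the CRF", and among the fields for each event are "Severity (mild, moderate, severe") and "Duration (start and end dates or whether they still exist at the time of the last inspection"). Its definition of an adverse event is limited to symptoms, signs or health conditions that are *unexpected*. Section 8.3.1 requires any adverse reaction to be entered on the adverse event form, without that limit.

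**The concern.** For harms, the reader of a trial report usually wants to know how bad the worst reaction was, how long the longest lasted, and how often reactions occurred. A mean of an ordinal grade answers none of these. It treats the steps between grades as equal, and it lets many trivial reactions offset one that mattered. A mean duration has the same weakness.

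Two features of the text add to this. The averaging unit is undefined, so seven centres could fill in the same item differently. And sections 7.2.2.2.12 and 8.1 describe the same symptoms in different terms: an average in one, a grade and dates per event in the other. The word *unexpected* in 8.1 leaves some room for a site to think that a foreseeable needling discomfort belongs only under 7.2.2.2.12.

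At stake is how informative the declared safety outcome will be, in a trial that names safety as an objective.

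**Working it through.** **Inputs**
- Sessions: 5 per week × 4 weeks = 20, which reproduces the total in section 5.2.
- Severity grades: mild, moderate, severe (section 8.1). The protocol gives them no numbers. *Assumption:* none = 0, mild = 1, moderate = 2.
- *Assumption:* section 7.2.2.2.12 uses the same three grades; it does not name its scale.
- Durations of 1 hour and 24 hours are illustrative, not trial data.

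The severity examples use a moderate reaction. Section 8.2 reserves *severe* for events that threaten life or cause death or disability and call for immediate withdrawal or emergency treatment. A severe reaction within a completed 20-session course is therefore unlikely on that scale.

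**Reading A: average over all 20 sessions**
- One moderate reaction, 19 sessions without symptoms: (2 + 19 × 0)/20 = 0.10.
- One moderate and 19 mild reactions: (2 + 19 × 1)/20 = 21/20 = 1.05.
- One 24-hour headache, 19 sessions without symptoms: 24/20 = 1.2 hours.
- One 24-hour headache and 19 of 1 hour: (24 + 19 × 1)/20 = 43/20 = 2.15 hours.

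**Reading B: average over symptomatic sessions only**

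With one moderate reaction and k mild ones, the mean is (2 + k)/(1 + k):

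| k mild reactions | Mean grade | Highest grade | Sessions affected |
|---|---|---|---|
| 0 | 2.00 | moderate | 1 |
| 1 | 3/2 = 1.50 | moderate | 2 |
| 4 | 6/5 = 1.20 | moderate | 5 |
| 19 | 21/20 = 1.05 | moderate | 20 |

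A lone reaction keeps its full grade. After that the score falls as the participant has more reactions: 2.00 for one moderate reaction, 1.05 for the same reaction plus 19 mild ones. The participant with more harm looks better. The last two columns do not have this fault.

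**Comparison of the readings.** The same participant, with one moderate reaction and nothing else, scores 0.10 under A and 2.00 under B. The documents do not say which applies.

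**Reading C: average intensity within one episode.** No dilution across sessions arises. The wording allows this reading too.

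**The case against.** The strongest reply is that the individual data are collected in any case. Section 8.1 requires a severity grade and dates for every adverse event, and section 8.3.1 sends any adverse reaction to the adverse event form. The highest grade per participant can be derived from those fields, and how safety data are tabulated is commonly left to a statistical analysis plan, which is not shown here. This stands in large part. A reader might infer that a severe or long reaction disappears from the data; the documents do not support that.

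A reader might also infer that a serious reaction is necessarily averaged down to mild. That is not supported either: it depends on an averaging rule the protocol does not state, and under readings B (for a lone reaction) and C it does not happen. Several important harms, including unbearable needling pain, fainting and infection, are listed before the discomforts to which the averages apply.

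A third tempting inference is that the average flatters the electroacupuncture arm, because only there is skin penetrated and current delivered. The protocol gives no reaction rates by arm, so the direction and size of any such effect are unknown.

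On the word *unexpected*, the document leans towards including the listed discomforts as adverse events. Section 7.2.2.2.12 follows them with *other* unforeseen adverse events, section 12 calls foreseeable needling reactions possible adverse events, and 8.3.1 has no such limit. The ambiguity is small, but one sentence removes it.

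What remains is that 7.2.2.2.12 itself names an average as the content of a declared outcome and leaves its unit undefined. A form built from that line could ask for an average, and from that field alone no later plan could recover the worst grade.

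**Conclusion.** The point holds as a minor but worthwhile correction to the safety summary. The average in section 7.2.2.2.12 is undefined. Taken across sessions, it can reduce one moderate reaction among 19 mild ones to 1.05, and one 24-hour headache among 19 of 1 hour to 2.15 hours. Taken over symptomatic sessions, it falls as mild reactions are added.

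The severity figures rest on assumed codes and on reactions at all 20 sessions, an extreme pattern chosen to show the mechanism. The duration figures need no coding but are also illustrative. The documents support neither a loss of safety data nor a bias towards one arm.

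**What to change.** In section 7.2.2.2.12:
1. Replace the averages with the severity and duration of each occurrence, taken from the section 8.1 fields.
2. Summarise them per participant as highest severity, longest duration and number of sessions affected.
3. State that the listed discomforts are entered on the adverse events page, notwithstanding the word *unexpected* in the 8.1 definition.

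The cost is small: a line or two of protocol text, a matching change to the case report form if it asks for averages, and a different summary table. Evaluation already takes place around every session, so no visits are added. The one downside is that the reported severity will look less favourable than a mean would. No clinical rule changes.

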7.2.2.13 Use of concomitant medications

The percentage of patients using concomitant medications and the changes in dosage

and frequency of concomitant medications (including rescue medication) is analyzed after the completion of the trial.

8. Safety assessment standard

8.1 Observation of adverse events

Adverse events are any unexpected symptoms, signs, or health conditions during the entire clinical study period (including washout period, observation period, routine treatment period, follow-up period, a total of 10 weeks), and may not have a causal relationship with the treatment in this study. Health conditions or diseases that existed before the start of this study can only be considered as an adverse event if they deteriorate further after starting the treatment of this study. Abnormal laboratory test values or test results can only be considered adverse events (AE) when they cause clinical symptoms or signs, are considered clinically significant or require treatment. Use non-inductive questions at each visit during the study period to discover adverse events from patients. Adverse events may also be reported by the patient during or between visits or discovered through physical examination, laboratory examination or other methods. All adverse events must be recorded on the adverse events page of the CRF, and the following information about the adverse events must be provided at the same time:

- Severity (mild, moderate, severe).
- The relationship with the research treatment (definitely related, very likely related, possibly related, definitely unrelated).
- Duration (start and end dates or whether they still exist at the time of the last inspection).
- Whether it is a serious adverse event (SAE). A serious adverse event (SAE) is defined as an adverse event leading to any of the following outcomes: 1) leading to death. 2) Fatal or life-threatening. 3) Lead to permanent or significant loss of

function or disability. 4) The patient needs to be hospitalized or the existing hospitalization time is extended, unless the hospitalization is due to: ① Conventional treatment or monitoring of research indications has nothing to do with any deterioration of physical condition; The disease undergoes elective or preplanned treatment, and the disease has not deteriorated after the application of the research treatment; ③In the outpatient and emergency department, the event did not meet the criteria for serious adverse events mentioned above, and did not lead to hospitalization; ④Social reasons And containment, and the patient' s general condition has not deteriorated. 5) Lead to congenital malformations or birth defects. 6) Other important medical events, that is, the event causes harm to the patient or may require medical or surgical intervention to prevent the occurrence of any one of the results listed in the above definition. Unlike conventional safety assessments, SAE requires continuous monitoring and special reporting requirements.

• All adverse events need to be dealt with correctly. Treatment methods may include one or more of the following methods: no measures are taken (that is, only further observation); study treatment adjustment/temporary interruption; permanent suspension of study treatment due to the adverse event; addition of combined drug treatment; non-drug treatment ; Allow the patient to be hospitalized or extend the patient's hospital stay. The measures taken to deal with adverse events shall be recorded on the adverse events page of CRF. Once an adverse event is found, follow-up until it is resolved or until it is determined that it is permanent, and at each follow-up (if necessary, the frequency of follow-up can be increased) changes in the severity of the adverse event, suspicious relationship with the treatment of this study, and the need The intervention means and results are evaluated.

8.2 Standards for judging the severity of adverse events

• Mild: The subject can tolerate it, does not affect the treatment, does not require special treatment, and has no effect on the subject's recovery.

- Moderate: The subjects are unbearable and need to withdraw the drug to suspend the test or do special treatment, which has a direct impact on the subjects' recovery.
- Severe: Endangering the life of the subject, causing death or disability, requiring immediate withdrawal or emergency treatment.

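### The adverse event severity grades in Protocol section 8.2 leave some events without a grade, overlap for others, and mix intensity with seriousness criteria and actions taken

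*Protocol*

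**What the plan says.** Protocol section 8.1 asks for several items on each adverse event. One is "Severity (mild, moderate, severe"); a separate one is "Whether it is a serious adverse event (SAE"). The SAE definition begins "1) leading to death. 2) Fatal or life-threatening. 3) Lead to permanent or significant loss of" and continues "function or disability". It then adds hospitalisation or its prolongation, birth defects and other important medical events. Section 8.1 also requires the measures taken for each event to be recorded on the CRF.

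Section 8.2 defines the grades:

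- The lowest grade, mild, is for an event that is tolerable, leaves both the study treatment and recovery unaffected, and calls for no special treatment.
- The middle grade is worded "Moderate: The subjects are unbearable and need to withdraw the drug to suspend the test or do special treatment"; it also expects recovery to be affected directly.
- The highest grade is worded "Severe: Endangering the life of the subject, causing death or disability, requiring immediate withdrawal or emergency treatment".

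The safety outcome in section 7.2.2.2.12 names the local events to be collected: "Contents include broken needles, fainting needles, unbearable acupuncture pain", the last with a threshold of VAS 8 or more. Section 8.3.1 lets the mode of follow-up depend on how severe a reaction is, and section 8.1 asks for changes in severity to be assessed at each follow-up.

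**The concern.** Severity describes how intense an event is; seriousness describes its outcome. Section 8.1 keeps the two apart, but section 8.2 builds the top grade mainly from outcomes and the middle grade partly from actions. Each grade bundles several conditions, so an event can fail all three grades or meet two.

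Safety is part of the stated objective (section 2), and 7 hospitals will apply the scale (section 3.1). Where the text gives no grade, or two, each site must decide for itself. Only the EA arm has skin penetration and current (sections 5.2 and 5.3), so needling-related harms should fall mainly in that arm. Inconsistent grading could therefore blur the comparison of severity between arms, in a direction that the protocol does not allow one to predict.

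**Working it through.** No figure in the protocol depends on these definitions, so the check is a logic table on the wording of section 8.2.

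**Step 1: events with no severe element.** Mild and moderate turn on three conditions: whether the event is tolerable, whether special treatment or withdrawal is needed, and whether recovery is affected. An effect on the study treatment is folded into the second. This gives 2 × 2 × 2 = 8 patterns.

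| Tolerable | Special treatment or withdrawal | Recovery affected | Grade |
|---|---|---|---|
| yes | no | no | mild |
| yes | no | yes | none |
| yes | yes | no | none |
| yes | yes | yes | none |
| no | no | no | none |
| no | no | yes | none |
| no | yes | no | none |
| no | yes | yes | moderate |

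Two patterns have a grade and 8 − 2 = 6 have none. If the recovery clauses are treated as description and ignored, 2 × 2 = 4 patterns remain. Two are graded and two are not: tolerable but treated, and unbearable but untreated. Those two gaps do not depend on how the recovery clause is read.

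**Step 2: the severe grade.** Its three phrases have no connecting word, so two readings are possible: (a) any one element suffices; (b) danger to life, death or disability is needed together with immediate withdrawal or emergency treatment. Take an event that already meets moderate in full and vary three factors: danger to life or death, disability, and immediate withdrawal or emergency treatment. There are again 8 patterns.

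- Reading (a): 1 pattern is moderate only; 8 − 1 = 7 are both moderate and severe.
- Reading (b): 3 patterns are both; 8 − 3 = 5 are moderate only.

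The grades overlap under either reading. With none of the three factors present, the event is moderate under both, however intense it is.

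**Step 3: severe against the SAE criteria.**

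| Element | Severe (8.2) | SAE (8.1) |
|---|---|---|
| Death | yes | yes |
| Danger to life | yes | yes |
| Disability | yes | yes |
| Immediate withdrawal or emergency treatment | yes | not listed as such |
| Hospitalisation or its prolongation | no | yes |
| Birth defect | no | yes |
| Other important medical event | no | yes |

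The overlap is large but not complete in either direction.

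**Step 4: the protocol's own example.** Unbearable needling pain with no severe element is moderate if it needs special treatment or withdrawal and affects recovery. It has no grade if it needs neither treatment nor withdrawal. If it forces immediate withdrawal and affects recovery, it is both moderate and severe under reading (a). The pain score does not decide between moderate and severe.

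**Step 5: the drug.** The interventions in section 5 are EA or SEA with lifestyle education. Sections 6.1 and 6.3 allow analgesics, but none is the study treatment, so the moderate grade's withdrawal condition has no clear referent.

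**The case against.** The strongest case against is that this is loose wording with little consequence. Investigators would probably grade a tolerable, treated event as moderate and, where two grades fit, take the higher. The 24-hour report in section 8.3.3 follows the SAE flag, not the grade. Measures taken are recorded separately, so treated events stay identifiable. Unbearable needling pain has its own threshold and is checked around each treatment, so it stays visible whatever its grade. The drug phrase looks like a translation slip.

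Most of this stands and limits the size of the point. It does not remove the gaps: the sensible grade has to be supplied against the text, and the protocol states no rule for taking the higher one.

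A reader might also infer more than the documents support:

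- *That any event which is not life-threatening is at most moderate.* A disabling event can be severe and, under reading (a), so can one needing immediate withdrawal or emergency treatment.
- *That severity and seriousness carry the same information, so that severe non-serious events are almost impossible.* Step 3 shows elements on each side that the other lacks. A hospitalised event can be an SAE graded moderate, and an event forcing immediate withdrawal can be severe without meeting a listed SAE criterion.
- *That the protocol contradicts itself by calling pain of 7-10 severe.* That band, in section 7.2.2.1, grades pain on the NRS-11 as the efficacy measure. It is not an adverse event scale.
- *That the severity results will understate needling harm.* The protocol specifies no such table and gives no event frequencies, so neither size nor direction can be stated.

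**Conclusion.** The point holds as a defect in a definition that the protocol itself states, not as a missing detail. The grades are neither exhaustive nor mutually exclusive, and severe largely repeats three SAE criteria that section 8.1 already captures. Without a severe element, 6 of 8 patterns are ungraded on the literal reading, and 2 of 4 if recovery is ignored. These count patterns in the wording, not expected events; how often the gaps arise is unknown.

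The conclusion assumes that the joined conditions in mild and moderate are all required, as written. It also takes special treatment, which the protocol does not define, to include ordinary non-emergency care. The consequence is limited to severity grading and the follow-up decisions that use it. It should be corrected, but no efficacy result, sample size, error rate or SAE-reporting rule rests on it.

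**What to change.** Reword section 8.2 and the adverse event page of the CRF so that severity is graded by intensity alone, in three categories that cover every event exactly once. Interference with usual activities is one possible basis; another intensity scale would serve if it meets the same condition. Leave death, danger to life and disability to the SAE flag in section 8.1. Leave treatment given and withdrawal to the measures-taken record that section 8.1 already requires, and remove the reference to a drug.

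This changes how events are classified, not who is treated or withdrawn. Where section 8.2 now ties withdrawal to a grade, the investigators need to reconcile it with section 4.4.

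The cost is a short amendment and a small CRF revision, with no added visits or staff. If the trial is under way, events already recorded need regrading, preferably by someone blind to group.
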